2.5 Bone Marrow Reticulin Evaluation in ITP

Reticulin is a normal component of the bone marrow that can be detected with reticulin (silver) stain (Thiele et al, 2005; Kuter et al, 2007). Increased reticulin (reticulin fibrosis) is associated with many benign conditions, while increased collagen fibrosis (detected by trichrome staining) is characteristic of myeloproliferative disease (Kuter et al, 2007). In a retrospective analysis of bone marrow biopsies from 40 patients with ITP, reticulin was present in approximately two-thirds of romiplostim-naïve patients (Mufti et al, 2006). Increased reticulin above normal levels may be observed with or without concomitantly increased collagen in several conditions. Increased reticulin without collagen fibrosis is associated with conditions such as hairy cell leukemia, human immunodeficiency virus infection, pulmonary arterial hypertension, and treatment with hematopoietic growth factors (Kuter et al, 2007).

Increased reticulin has been observed following treatment with recombinant human thrombopoietin (rHuTPO), interleukin-3, and interleukin-11 (Kuter, 2007; Kuter et al, 2007), and is likely a response to stimulation of megakaryocytes by thrombopoietin (TPO) (Douglas et al, 2002), or related to cytokines or other factors that are elaborated by the megakaryocytes (Castro-Malaspina et al, 1981; Yanagida et al, 1997; Schmitt et al, 2000). Bone marrow reticulin (or the presence of reticulin on study) was observed in 3.7% (10 of 271) of subjects evaluated who had received romiplostim for ITP [data on file]. Increased reticulin formation may be due to the increased number of megakaryocytes in the bone marrow as a result of romiplostim treatment, consistent with findings associated with other thrombopoietins (Kuter, 2007).

Recent evidence has shown that the amount of bone marrow reticulin detected by silver staining often exhibits no correlation to disease severity, while the presence of type 1 collagen, as detected by trichrome staining, is often associated with more severe disease, a poorer prognosis (Kuter et al, 2007), and may be associated with malignant conditions such as chronic idiopathic myelofibrosis (Tefferi, 2005).

To prospectively evaluate the incidence of both reticulin and collagen formation in the bone marrow during treatment with romiplostim, a trial in adults with ITP receiving open label romiplostim for up to 3 years is in progress (Amgen study 20080009). Three cohorts of subjects will undergo repeat bone marrow evaluation after 1, 2, or 3 years to evaluate the incidence and potential sequelae of reticulin and collagen formation in the bone marrow. To date, no development of collagen has been seen in cohorts 1 (1 year) and 2 (2 years). Increase by 2 grades in reticulin has been observed in no subjects in

Product: Romiplostim
Protocol Number: 20101221
Date: 15 August 2014

Page 19 of 69

cohort 1 and 2 subjects in cohort 2. Cohort 3 evaluations are in progress. Bone marrow studies of children with ITP to evaluate reticulin and collagen formation have not previously been conducted.

2.6 Anti-romiplostim Antibody Results

To date, anti-romiplostim neutralizing antibodies have been detected in samples from 2 adult subjects with ITP. One of the subjects presented with anti-romiplostim neutralizing antibodies at the end of study (EOS) time point but tested negative for neutralizing antibodies to romiplostim on follow-up 4 months later (after discontinuation of romiplostim). The second subject had neutralizing antibodies to romiplostim at an unscheduled time point after dosing with romiplostim but tested negative for neutralizing antibodies to romiplostim at 2 follow-up time points (week 132 and EOS) after discontinuation of romiplostim. No cross-reactive binding antibodies to TPO were observed.

For a complete summary of all safety and efficacy data collected in both the adult and pediatric ITP indications for the romiplostim clinical development program, please refer to the most recent version of the [Romiplostim Investigator's Brochure](#).

2.7 Pediatric Risk Assessment

Previously reported safety results of the earlier phase 2 study (20060195), the currently enrolling phase 3 study (20080279), and open-label long-term follow-up study (20090340) support a favorable benefit risk profile with the use of romiplostim in thrombocytopenic pediatric subjects. This study represents the fourth investigation of romiplostim in thrombocytopenic pediatric subjects with ITP.

2.8 Rationale

The treatment of ITP in pediatric patients is warranted to prevent clinically significant bleeding events, especially intracerebral hemorrhage. The management of children with ITP who either fail to respond to treatment or relapse following splenectomy is often challenging. It is recognized that multiple therapeutic options are available and can be used as a single agent or in combination. However, the sustained remission rate with monotherapy has proved disappointing, and controlled studies have not been performed. Furthermore, small studies have demonstrated the potential for improved outcomes with combination therapy, but there is no accepted standard of care ([Robb and Tiedeman, 1990](#)). Appreciating the toxicities associated with many of the available treatments and knowing the limitations of current therapies, including failure after splenectomy, the management of pediatric ITP remains medically challenging.

Product: Romiplostim
Protocol Number: 20101221
Date: 15 August 2014

Page 20 of 69

Treatment with a thrombomimetic therefore represents a unique opportunity to treat this challenging disease with a novel therapy. The route of administration, schedule, starting dose, and subsequent dose adjustments of romiplostim have been well established in previous pediatric and adult ITP studies and will be used for dosing and administration in this protocol. Romiplostim will be administered initially in the clinic by a qualified health care provider as a subcutaneous injection. The starting dose of romiplostim will be 1 µg/kg/week based on the subject's recorded screening weight. Throughout the treatment period, subjects will return to the clinic to provide platelet counts and undergo dose titrations under the supervision of the treating physician. Weekly dose increases will continue in increments of 1 µg/kg up to a maximum dose of 10 µg/kg in an attempt to reach a target platelet count of $\geq 50 \times 10^9/L$. Dose adjustments will be allowed to maintain a platelet count between $\geq 50 \times 10^9/L$ and $\leq 200 \times 10^9/L$.

2.9 Clinical Hypotheses

No formal hypothesis will be tested in this study. The percentage of time with a platelet count $\geq 50 \times 10^9/L$ in the first 6 months of the study will be estimated.

3. EXPERIMENTAL PLAN

3.1 Study Design

This is a phase 3b single arm, open-label, multicenter study evaluating the percentage of time pediatric subjects with ITP have a response while receiving romiplostim, defined as a platelet count $\geq 50 \times 10^9/L$ and in the absence of ITP rescue medications in the past 4 weeks. This protocol will provide open-label romiplostim to thrombocytopenic pediatric subjects with ITP diagnosed for at least 6 months and who have received at least 1 prior ITP therapy (excluding romiplostim) or are ineligible for other ITP therapies.

The study design consists of a 4-week screening period, up to a 3-year treatment period, an end of treatment (EOT) visit, and an end of study (EOS) visit.

Subjects entering the study on medications to raise platelet counts may remain on these concomitant medications, as needed, along with romiplostim. After the initiation of romiplostim, if subjects require additional medications to raise platelet counts, or an increase in dose of existing medications, rescue ITP therapies may be initiated (see [Section 6.4](#)). If the subject's platelet count is $\geq 50 \times 10^9/L$, concomitant or rescue ITP therapies can be reduced or discontinued.

Product: Romiplostim
Protocol Number: 20101221
Date: 15 August 2014

Page 21 of 69

Approximately 200 subjects with ITP will be enrolled and will receive weekly romiplostim until they complete the study, discontinue participation in the study for any reason, or the study ends.

The overall study design is described by a [study schema](#) at the end of the protocol synopsis section.

The study endpoints are defined in [Section 10.1](#).

3.1.1 Subjects With an Onset of Sustained Platelet Response

During the treatment period, romiplostim doses will be adjusted as outlined in [Table 1](#). Subjects who dose reduce romiplostim such that they no longer require treatment with romiplostim, no longer require ITP medications (concomitant or rescue), and have an onset of a sustained platelet response (defined as a consecutive platelet counts $\geq 50 \times 10^9/L$) will be monitored for at least 6 months beginning with the first platelet count $\geq 50 \times 10^9/L$. Subjects whose platelet count remains $\geq 50 \times 10^9/L$ in the absence of any medications for ITP for at least 6 months will then be followed every 12 weeks for the duration of the 36-month treatment period.

If during the 36-month treatment period the platelet count subsequently falls below $< 50 \times 10^9/L$, treatment with romiplostim at the initial starting dose may be resumed. Subsequent doses will be adjusted as shown in [Table 1](#). Clinic visits will be resumed per the Schedule of Assessments ([Table 2](#)).

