3.5 Estimated Study Duration

3.5.1 Study Duration for Participants

For an individual subject, the length of participation includes a 4-week screening period, up to a 36-month treatment period, an EOT visit, and an EOS visit. The maximum duration for a subject completing the study will be approximately 3 years and 2 months.

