7.6 Romiplostim Treatment Period (Up to a 36 Months Duration)

Subjects that meet all study entrance criteria will be enrolled using IVRS to receive romiplostim.

The following procedures will be completed during the romiplostim treatment period at the times designated in the Schedule of Assessments ([Table 2](#)):

- documentation of concomitant and rescue medications
- adverse event reporting
- central lab CBC with differential (every 4 weeks)
- central lab blood chemistry (every 12 weeks)
- local lab platelet counts.
- collection of blood samples for anti-romiplostim antibodies (first sample is collected before first dose of romiplostim, then at week 12, week 52, and every 24 weeks thereafter)
- local lab peripheral blood smear (every 4 weeks)
- physical exam with vital signs and weight (every 12 weeks)
- local lab urine or serum pregnancy test for female subjects of child-bearing potential (defined as having first menses) every 12 weeks
- romiplostim administration

Note: Administration of romiplostim should be the last procedure completed during each visit that it is required.

For the first 8 weeks of treatment, all subjects will return to the clinic for weekly administration of romiplostim. Subjects who have received their first 8 doses in the clinic and achieve a stable dose of romiplostim for at least 4 weeks may be allowed to self-inject romiplostim or have the injection administered by a caregiver. For subjects who established a stable dose of romiplostim and are self-administering, platelet counts will be monitored every 4 weeks. For complete details on self-administration, refer to [Section 6.3](#). Subjects who stop romiplostim and all other medications for ITP (concomitant or rescue) due to the onset of a sustained platelet response will continue to be monitored per the schedule of assessments for at least 6 months from the first platelet count $\geq 50 \times 10^9/L$.

Product: Romiplostim
Protocol Number: 20101221
Date: 15 August 2014

Page 39 of 69

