7.7 End of Treatment Visit (EOT)

All subjects will complete an EOT visit. For subjects who complete the 36-month treatment period and who have been off romiplostim and other medications for ITP (concomitant or rescue) for 4 weeks or more, the EOT visit will be the final study visit and will occur after the completion of the 36-month treatment period. For subjects ending the 36-month treatment period for non-response or other reasons while still receiving romiplostim, this visit will be 1 week after the last administration of romiplostim.

The following assessments will be completed at the EOT visit:

- physical exam, including vital signs
- documentation of concomitant and rescue medications
- adverse event reporting
- central lab CBC with differential and blood chemistry
- local lab platelet counts
- collection of blood samples for anti-romiplostim antibodies
- local lab peripheral blood smear
- local lab urine or serum pregnancy test for female subjects of child-bearing potential (defined as having first menses)

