7.8 End of Study Visit (EOS)

Four weeks after the last dose of romiplostim for subjects who end the 36-month treatment period for non-response or other reasons while still receiving romiplostim will have an EOS visit.

The following assessments will be completed at the EOS visit:

- local lab platelet count
- serious adverse event reporting
- documentation of concomitant and rescue medications

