#### 4.4 Exploratory Endpoints

- The subject incidence with a sustained platelet count of  $\geq 50 \times 10^9/L$  for 6 months or greater without any use of ITP medications (concomitant, rescue, or romiplostim )
- An onset of a sustained platelet response is defined as consecutive platelet counts  $\geq 50 \times 10^9/L$  in the absence of any ITP medications (including romiplostim and other concomitant or rescue medications for ITP). Number and percentage of subjects who have an onset of a sustained platelet response and maintained for at least 24 weeks are summarized.
- The incidence of splenectomy during the treatment period for subjects entering the study pre-splenectomy
- Number and percentage of subjects who did not undergo a splenectomy before study enrollment and had a splenectomy during treatment period are summarized.
- The subject incidence of romiplostim self-administration
- Number and percentage of subjects who initiated self-administration during treatment period are summarized.

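### Exploratory sustained-response endpoint: drug-free onsets after about month 30 to 31.6 cannot complete 6 months (or 24 weeks) of observation, and the SAP's crude percentage does not separate these children from relapses

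*Protocol*

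**What the plan says.** The endpoint is exploratory (Protocol 1.3 and 10.1.1; SAP 2.3 and 4.4). It is the subject incidence of platelet counts at or above 50 x 10^9/L kept up for 6 months or more off all ITP medication, romiplostim included.

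**Monitoring after onset.** Protocol 3.1.1 says such a child "will be monitored for at least 6 months beginning with the first platelet count" at or above the threshold. Section 7.6 repeats this: these children "will continue to be monitored per the schedule of assessments for at least 6 months from the first platelet count" at that level. Neither section makes an exception for an onset near the end of the study. Children who complete the 6 months "will then be followed every 12 weeks for the duration of the 36-month treatment period".

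**End of follow-up.** For a child who completes 36 months and has been off romiplostim and other ITP medication for at least 4 weeks, Protocol 7.7 states that "the EOT visit will be the final study visit and will occur after the completion of the 36-month treatment period". The later visit in 7.8 is for children still receiving romiplostim when treatment ends: "Four weeks after the last dose of romiplostim for subjects who end the 36-month treatment period". Protocol 3.5.1 gives the overall limit: "The maximum duration for a subject completing the study will be approximately 3 years and 2 months". That figure includes screening.

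**Analysis.** SAP 4.4 plans: "Number and percentage of subjects who have an onset of a sustained platelet response and maintained for at least 24 weeks are summarized". SAP 10.5 describes the same simple proportion, and SAP 7.3 bases efficacy analyses on all children who received at least one dose. Neither section has a censoring rule, a not-assessable category or a bound. SAP 9.3 covers missing dates and missing platelet counts, but not observation that stops before 24 weeks.

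**The concern.** The endpoint needs a fixed length of observation after onset, and onset can come at any time in the 36 months. A child whose drug-free response begins at month 33 and is intact at the last visit has about 3 months observed. In a plain proportion that child falls outside the numerator, together with children whose counts dropped below 50 or who restarted treatment. A child who leaves the study while in drug-free response lands in the same place.

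A reader of the table could not tell how many of the children with an onset lost the response and how many were simply not watched for long enough. There is also a practical side: a site with a late-onset child finds a stated minimum of 6 months of monitoring in two sections and an earlier final visit in two others.

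**Working it through.** **1. Reproduce the plan's own duration.** Inputs: screening 4 weeks and treatment 36 months (Protocol 3.5.1); last visit 4 weeks after the last dose (7.8). With 1 month = 365.25/12 = 30.44 days, 4 weeks = 28/30.44 = 0.92 month.

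0.92 + 36 + 0.92 = 37.8 months, against 38 months (3 years 2 months) stated. The figure reproduces.

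**2. Latest onset that can qualify.** Formula: end of follow-up after day 1, minus the required drug-free time. The required time is 6 months (protocol) or 24 weeks = 168/30.44 = 5.52 months (SAP).

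| End of follow-up after day 1 | 6-month rule | 24-week rule |
|---|---|---|
| Month 36 (Protocol 7.7) | 36 - 6 = 30.0 | 36 - 5.52 = 30.5 |
| Month 37.08 (38 - 0.92, the whole of 3.5.1) | 31.1 | 31.6 |

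The cut-off therefore lies between month 30 and month 31.6. Example: an onset at month 33 needs observation to month 39. With screening that is 39 + 0.92 = 39.9 months of participation, against 38 stated.

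**3. Share of onsets that come too late.** The documents give no distribution of onset times, so these are assumptions. The cut-off is month 30, the earliest of the four, which gives the largest shares.

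- Uniform from month s to month 36, share = 6/(36 - s): s = 1 gives 6/35 = 17%; s = 3 gives 6/33 = 18%; s = 6 gives 6/30 = 20%.
- Exponential from month 2, share = [F(36) - F(30)]/F(36): medians of 6, 12, 18, 24 and 36 months give 2.0%, 6.8%, 9.6%, 11.3% and 13.2%.

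The range is 2% to 20%. It depends on onsets beginning by month 6: uniform onsets starting only at month 12 would give 6/24 = 25%. With the latest cut-off (month 31.6), the uniform shares for s = 3 and s = 6 fall to 13% and 15%.

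**4. Effect on the reported percentage.** Assume 40 onsets among the planned 200 children; the 40 is an assumption.

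- 2%: 40 x 0.02 = 0.8 child; 0.8/200 = 0.4 point.
- 20%: 40 x 0.20 = 8 children; 8/200 = 4 points.

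These are maxima for each scenario, because they treat every late onset as one that would have lasted. If half would have lasted (an illustration), the figures are 0.2 and 2 points. Children who drop out while in response are not included and would add to the unassessable count.

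**The case against.** Several objections have force.

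*The endpoint is exploratory and the study descriptive.* This stands. No hypothesis is tested. The primary endpoint covers the first 6 months of treatment, and neither it nor the sample size is touched.

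*The percentage is not biased.* A reader might infer that the planned figure is biased low and that the SAP scores late onsets as failures. The documents do not support this. The SAP never labels these children failures, and neither document sets as its target the proportion who would eventually sustain a response. Read as completed sustained response observed on study, the percentage is correct, and a month-33 onset is simply not yet an event. What remains is that the table does not show how many children are in that position.

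*The monitoring text does not conflict with the visit schedule.* Section 3.1.1 opens by referring to the treatment period, 7.6 is headed as lasting up to 36 months, and Table 2 footnote b uses the completed 6 months as the condition for moving to 12-weekly visits. On that reading, the 6 months governs when visits may thin out within the 36 months and promises nothing afterwards. Section 7.7 fixes no exact date, and the limit in 3.5.1 is approximate. This reading is tenable, so a flat contradiction is not proven. But both monitoring statements are unqualified, and the text does not say which reading applies.

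*Kaplan-Meier changes the question.* Correct: among children with an onset it estimates durability given onset, not incidence, and it assumes that leaving the study in response is unrelated to later relapse. It can only supplement the percentage.

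**Conclusion.** The point holds as a cheap improvement to an exploratory table, plus a protocol clarification. On the scheduled visits, drug-free onsets after about month 30 to 31.6 cannot meet the 6-month or 24-week requirement. The planned percentage is sound for completed responses observed on study. If every child with an onset is meant to count, it is a lower bound, because a child still in response with short observation can only be missing from the numerator.

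The size is uncertain: 2% to 20% of onsets unassessable, and at most about 0.4 to 4 percentage points of 200 children. Both ranges rest on assumed onset distributions, and the second also on an assumed 40 onsets. The calendar cut-off rests only on the documents' own figures.

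**What to change.** 1. In SAP 4.4 and 10.5, keep the crude number and percentage. Add a separate count of children still in drug-free response with under 24 weeks observed, split into late onset and dropout in response.
2. Report two bounds: all of those children counted as failures (which equals the crude percentage) and all counted as successes. The bounds need no assumption about why observation stopped.
3. Optionally, add a Kaplan-Meier estimate from onset of the probability of maintaining response. The event is the first count below 50 or a restart of any ITP medication, with censoring at the last platelet count. Label it as durability conditional on onset under non-informative censoring. Define the onset date first: neither document says how many consecutive counts make an onset, and starting at the first of them builds in a short event-free interval.
4. Reconcile Protocol 3.1.1 and 7.6 with 7.7 and 3.5.1 on how long a late-onset child is observed. Which rule should apply is for the sponsor to decide.

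Cost: some SAP wording, one extra table from platelet and medication dates already collected, and a protocol clarification. The analysis changes need no extra visits or children. The downside is that some children are reported as not assessable.

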3.1.2 Non-responding Subjects

Subjects who have a platelet count $\leq 20 \times 10^9/L$ for 4 consecutive weeks at the maximum romiplostim dose of 10 $\mu\text{g}/\text{kg}$ should be discontinued from romiplostim and will be considered non-responders. If the subject is a non-responder but the investigator believes the subject has obtained clinical benefit, the investigator must contact the Amgen medical monitor for the subject to continue participation in the study.

3.2 Number of Centers

There will be approximately 50 centers located in (but not limited to) Australia, Canada, Europe, Israel, South Africa, South America, and the United States.

Sites that do not enroll any subjects within 6 months of site initiation may be closed.

Product: Romiplostim
Protocol Number: 20101221
Date: 15 August 2014

Page 22 of 69

